**C. Study Design and Approach. (RQ-2, RQ-3, RQ-4, RQ-5, RQ-6)**

We will use a three-group randomized trial design to compare the effectiveness of two theory-based interventions to promote completion of CRC screening among individuals at average risk for CRC and, for those who complete colonoscopy, high quality bowel preparation. We will enroll an ethnically diverse group of 450 men and women who canceled, or did not attend, their colonoscopy appointment and randomize them to receive: 1) a tailored DVD intervention; 2) the tailored DVD *plus* a patient navigator intervention; or 3) usual care. The aims of this study are to:

**1. Compare the effectiveness of two interventions designed to promote CRC screening among people at average risk for CRC - a tailored DVD versus the tailored DVD *plus* telephone-based patient navigation - to each other and to usual care.**

Hypothesis 1.1: Participants who receive the tailored DVD *plus* telephone-based patient navigation intervention will have higher rates of colorectal cancer screening with fecal immunochemical test (FIT), colonoscopy, or either screening test compared to those who receive the tailored DVD alone.

Hypothesis 1.2: Participants who receive either intervention will have higher rates of colorectal cancer screening with fecal immunochemical tests (FIT), colonoscopy, or either screening test than those who receive usual care.

[figure not shown]
Hypothesis 1.3: Participants who receive either intervention who complete colonoscopy will have: 1) better quality of bowel preparation; 2) less anxiety about the procedure; and 3) greater satisfaction with the colonoscopy experience than those who receive usual care.

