**PRIMARY OUTCOME MEASURES: (RQ-6, PC-2, IR-4)**

**Completion of any CRC screening test** (fecal immunochemical test (FIT) or colonoscopy) will be measured by medical record review. FIT and colonoscopy completion dates will be extracted from the electronic medical record. Because self-report of CRC screening has correlated well with medical record data, we will also use validated items from our previous research to ask participants if they have had a CRC screening test (FIT or colonoscopy) as well as their plan to have one in the next 6 months (only for those who have not yet completed screening).

**Quality of bowel preparation** will be assessed two ways for those participants who attend their colonoscopy: 1) by participant self-report of their bowel prep experience and 2) via review of electronic medical records. When patients arrive in the endoscopy department, a nurse assesses their experience with the bowel preparation and adherence to dietary restrictions. Patients who report they were unable to complete the bowel prep or have eaten in the past 24 hours are considered inadequately prepped for the procedure and sent home. These patients must repeat the preparation to cleanse the bowel and reschedule their colonoscopy. For those who report successful completion of the bowel prep and adherence to dietary restrictions, quality of the bowel preparation (i.e. degree of cleanliness/emptiness of the bowel) is evaluated by the endoscopist during the colonoscopy. Standard practice is to evaluate bowel preparation quality using an assessment similar to the Aronchick 5-point scale where 1=*excellent*, 2=*good*, 3=*fair*, 4=*poor*, and 5=*inadequate*. Adequate is a term that may also be used to describe the quality of bowel preparation as a single descriptor or in addition to the Aronchick assessment as excellent (1), good (2), or fair (3). Procedural notes including endoscopists' ratings of the quality of the bowel prep are entered into ProVation, a menu-driven software program. Therefore, participants will be considered inadequately prepped if they are: 1) deemed inadequately prepped from self-report during initial nursing assessment OR 2) if the endoscopist rates the quality of the bowel prep as poor (4)

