For Aim 1, we will test the primary hypothesis related to comparing intervention effects among the three randomized groups (H1.1: PN+DVD vs. DVD only and H1.2: PN+DVD vs. usual care and DVD only vs. usual care) using the outcome of completion of CRC screening using any test at 12 months post-baseline. In addition, quality of bowel preparation, procedural anxiety, and satisfaction with the screening experience will be examined as outcomes. As an initial assessment of CRC screening completion at 12 months, we will use a chi-square test for a 3 x 2 (group by screening completion) contingency table to test whether completion rates differ across groups. If the  $p$ -value for the overall test is significant at the .05 level, pair-wise 2 x 2 tests will be conducted at the  $.05/3 = .017$  level. However, the primary analyses for Aim 1 will involve fitting multivariable logistic regression models of the primary outcome of 12-month CRC screening test completion (yes/no). Independent variables will be group assignment and continuous and categorical individual characteristics. These models will also allow us to investigate intervention effects on CRC screening test completion while adjusting for potential confounders. Group assignment will be coded using dummy variables with usual care as the reference category. For H1.3, quality of bowel preparation will be analyzed for those participants who complete colonoscopy with proportional-odds ordinal logistic regression using an ordinal dependent variable ( $1 = \text{excellent}$ ,  $2 = \text{good}$ ,  $3 = \text{fair}$ ,  $4 = \text{poor}$ ,  $5 = \text{inadequate}$ ). If some outcome categories are sparse, the outcome will be dichotomized into adequate

(*excellent or good*) versus inadequate (*fair, poor, or inadequate*). The outcomes of anxiety and satisfaction are continuous outcomes and will be modeled with linear regression.

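### Section C.9 counts a failed nursing check as inadequate bowel preparation, but H1.3 and C.13 analyse only colonoscopy completers, so a participant sent home who never completes is a failure by definition yet absent from the analysis

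*Combined protocol and SAP*

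**What the plan says.** The detailed definition in C.9 (Primary Outcome Measures, quality of bowel preparation) sets the population as attenders: preparation "will be assessed two ways for those participants who attend their colonoscopy". Patients who fail the nurse's questions on arrival "are considered inadequately prepped for the procedure and sent home". C.9 continues: "These patients must repeat the preparation to cleanse the bowel and reschedule their colonoscopy". Only those who pass are rated by the endoscopist. A participant then counts as inadequately prepared on either of two limbs: if "deemed inadequately prepped from self-report during initial nursing assessment OR" if the endoscopist gives a rating of poor (4) or inadequate (5).

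Three other places use a narrower population. Hypothesis 1.3 reads "Participants who receive either intervention who complete colonoscopy will have: 1) better quality of bowel preparation". The opening summary of C.9 limits the outcome to people who complete colonoscopy. C.13 (Aim 1) states that "quality of bowel preparation will be analyzed for those participants who complete colonoscopy with proportional-odds ordinal logistic regression", on a scale from 1 (excellent) to 5 (inadequate). If categories are sparse, C.13 falls back to excellent or good versus fair, poor or inadequate. Neither the ordinal model nor the fallback mentions the nursing check. No section says how a sent-home participant is coded, or which attempt counts if that person later completes.

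**The concern.** C.9 lists quality of bowel preparation among the primary outcomes, and arriving adequately prepared is one of the things both interventions are built to improve. The DVD gives preparation instructions (C.4.a), and the navigator calls shortly before the appointment about preparation and diet (C.4.b). Arriving unprepared is one of the plan's own two forms of failure, and the completers-only rule removes it for anyone who does not come back.

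Whether a sent-home participant comes back is itself something an intervention may change. Navigators make as many contacts as completion requires, and they exist only in the DVD plus navigation arm. A completers-only comparison can therefore mix quality of preparation with persistence after a failed visit. The screening-completion outcome is not affected.

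**Working it through.** **1. Side by side.**
- *Sent home, never completes.* C.9: inadequate, by the nursing-check limb. C.13: not in the analysis set. This follows directly from the text.
- *Sent home, returns and completes.* C.9: its rule is worded for the participant, so the first failure can be read as deciding. C.13: the person is in the set, but the attempt to be used is not stated. Taking the completed examination's rating leaves the first failure uncounted; carrying the C.9 rule forward gives category 5.
- *Passes the check and is examined.* Both sections use the endoscopist's rating, except that the C.13 fallback cuts the scale elsewhere: a rating of fair is on the adequate side in C.9 and on the inadequate side in C.13.

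**2. The plan's own figures.** The plan gives no calculation specific to bowel preparation. C.12 says only that power for it will most likely exceed 80%, reasoning from the full sample. Table 4 (any-test completion, n = 115 per arm, two-sided α = 0.017) does reproduce, using the two-proportion formula with continuity correction:

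power = Φ{[d − 1/n − z√(2p̄(1−p̄)/n)] / √[(p₁(1−p₁)+p₂(1−p₂))/n]}

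This gives 92.2%, >99.9% and 81.0%, against 92%, 99% and 80% stated. The planned rates can therefore be used as they stand.

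**3. How many completers.** Any-test completion is an upper bound on colonoscopy completion, since some participants will choose FIT.
- At 115 per arm: 115 × 0.44 = 50.6; 115 × 0.20 = 23.0; 115 × 0.05 = 5.75. That is at most about 51, 23 and 6.
- At all 150 per arm: 66, 30 and 7.5.

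With about six completers in usual care, one or two sent-home participants could move the comparison.

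**4. Illustration on assumed rates** (none is in the documents). Let s be the proportion of attenders sent home, and q the proportion rated poor or inadequate at any examination, equal in both arms. Suppose the intervention changes only s. The C.9 failure rate is s + (1 − s)q.
- s = 5% (intervention) vs 20% (usual care), q = 10%: 14.5% vs 28.0%, a difference of 13.5 points.
- Same s, q = 20%: 24.0% vs 36.0%, a difference of 12.0 points.
- s = 10% vs 30%: differences of 18 points (q = 10%) and 16 points (q = 20%).
- s = 15% in both arms: no difference between arms. The C.9 rate is 23.5% or 32.0%.

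Under C.13, if returners take the rating of the completed examination, the rate among completers is q in both arms. The difference is then 0 in every row, whatever share returns.

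If returners are instead coded 5, the result depends on the share r who return: rate = [(1 − s)q + rs] / [1 − s(1 − r)]. For s = 5% vs 20%:
- r = 0: difference 0.
- r = 50%, q = 10%: 0.120/0.975 = 12.3% vs 0.180/0.900 = 20.0%, a difference of 7.7 points.
- r = 50%, q = 20%: 0.215/0.975 = 22.1% vs 0.260/0.900 = 28.9%, a difference of 6.8 points.
- r = 100%: the full 13.5 or 12.0 points.

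The same data can thus give anything from no difference to the whole C.9 difference, depending on an unstated coding rule and on who returns.

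**The case against.** **H1.3 is itself about completers, so the analysis matches the hypothesis.** It does, and that stands as a description of H1.3. It leaves both in conflict with the detailed C.9 definition, which starts from attenders and includes a failure that prevents completion at that visit.

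**Intent-to-treat covers it.** The general statement in C.13 includes all participants regardless of compliance, but the specific population given for this outcome overrides it.

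**Staff could code a failed check as category 5.** C.13 names no rater, so this is open for returners. It cannot bring in people who never complete.

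**The failure is not lost to the trial.** Someone sent home who never returns and does no FIT counts as unscreened in the main outcome. True, but that does not measure preparation.

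**Usual care is not left without support.** C.4 and E.2 describe rescheduling instructions and a reminder call, and in C.4 that call also answers preparation questions. The repeat-and-rebook rule in C.9 applies to every patient, and for DVD only versus usual care the documents describe no difference in rebooking help. This stands, and it limits what can be said about differences between arms.

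**Conclusion.** The point holds as an inconsistency between the outcome definition and the analysis population. Exclusion of sent-home participants who never complete is certain from the text. For returners the defect is silence about which attempt counts.

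Four stronger readings are tempting and are not supported:
- *Failures reappear as successes.* C.13 does not say so, and a repeat examination may again be rated poor or inadequate.
- *The loss differs by arm in a known direction.* Navigator support makes a difference plausible for DVD plus navigation against the other arms, but nothing shows it. If repeat preparations are rated differently from first ones, the distortion could also run another way.
- *The loss can be sized from the Background's figure of up to 30% of attenders inadequately cleansed.* That figure is pooled over patients and not split between sent-home and poor rating. It may describe examination findings only, and it says nothing about a between-arm effect.
- *The reported inadequacy rate will be too low.* At the C.9 cut-off, with returners taking the repeat rating, it cannot exceed the C.9 rate. The C.13 fallback adds fair to the inadequate side, which pushes the other way.

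The 0 to 18 point range in the illustration rests wholly on assumed sent-home, return and rating rates. The count of at most about 51, 23 and 6 completers rests on the plan's own rates at 115 per arm.

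**What to change.** - Define the bowel-preparation outcome in all participants who attend a colonoscopy appointment after baseline, at the first attended appointment.
- Code failure at the nursing check as the worst category (inadequate). Otherwise use the endoscopist's rating from that visit.
- Keep the endoscopist rating among completers as a supportive analysis, and tabulate by arm the numbers attending, sent home, returning and completing.
- Align H1.3, the C.9 summary and C.13 with this population.
- Confirm that the record review abstracts visits that ended without a procedure. C.7 says the arrival questions are documented in the EMR and Table 3 schedules review of preparation quality, but no section says that sent-home visits are extracted.
- Reconcile the treatment of fair between C.9 and the C.13 fallback.

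The cost is modest: wording, a coding rule and possibly a small extension of the chart abstraction, with no new contact with participants. There are three downsides. The population in the wording of H1.3 changes. The lowest category mixes failures determined by a nurse with failures determined by an endoscopist. The analysis still conditions on attendance after randomisation, which the interventions aim to change, so selection is reduced but not removed.

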**Table 3: Data Collection Timeline**

Measures	Baseline Interview (T1)	Process Interview (2 weeks after mailing DVD)	Follow-up Interview at 6 months post-baseline (T2)	Final Interview at 9 months post-baseline (T3)	12 months post-baseline (Final medical record review)
Demographics, social support, media exposure	X				
Health literacy, health status to include co-morbidities	X				
CRC screening experience and readiness to screen, patient activation, health beliefs (perceived CRC risk, benefits of screening, barriers to screening, self-efficacy for screening), CRC fear, cancer fatalism	X		X		
Colonoscopy-related procedural anxiety	X		X	X	
CRC and screening knowledge	X		X		
Receipt, viewing and satisfaction with the DVD		X			
Receipt, experience & satisfaction with the PN			X		
Self-report of CRC screening intention and completion			X	X	
Satisfaction with the screening experience			X	X	
Trial participation feedback				X	
Medical record review: CRC screening test completion, quality of bowel preparation			X	X	X

**C.9. Measures.** The primary study outcomes of CRC screening completion with any test (FIT or colonoscopy), and quality of bowel preparation (for those who complete colonoscopy), colonoscopy-related procedural anxiety and satisfaction with the CRC screening experience are described in this section. Secondary outcomes of the interventions include changes in knowledge and health belief variables (perceived risk, benefits, barriers, and self-efficacy). Other measures include patient activation, CRC fear, cancer fatalism, and satisfaction with the interventions. Measures have been extensively tested and refined in preliminary studies, and are described in more detail elsewhere.

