or inadequate (5). Eskeanzi Health is introducing the Boston Bowel Preparation Scale (BBPS) as another type of bowel preparation quality measure. The BBPS measures quality on a 10 point scale of 0-9. BBPS evaluations will also be entered into ProVation by the endoscopist and compared to the Aronchick findings. A decision will be made at a later time as to whether or not the BBPS ratings will be included in reporting this study outcome.

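### The sparse-category fallback in C.13 counts 'fair' bowel preparation as inadequate, the C.9 outcome definition does not, and no rule says how an 'Adequate'-only record is coded

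*Combined protocol and SAP*

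**What the plan says.** **C.9 (Measures, quality of bowel preparation).** The section lists "quality of bowel preparation (for those who complete colonoscopy") among the primary study outcomes. The endoscopist grades on a five-point scale from 1 (excellent) to 5 (inadequate), with fair as 3. A participant counts as inadequately prepared on either of two limbs: "deemed inadequately prepped from self-report during initial nursing assessment OR 2) if the endoscopist rates the quality of the bowel prep as poor (4"). Grade 5 belongs to the second limb too. Fair is on neither.

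C.9 also says: "Adequate is a term that may also be used to describe the quality of bowel preparation as a single descriptor". The alternative is to use the word "in addition to the Aronchick assessment as excellent (1), good (2), or fair (3"). A patient found unprepared at the nursing assessment is sent home: "These patients must repeat the preparation to cleanse the bowel and reschedule their colonoscopy".

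**C.13 (Data Analyses, Aim 1, H1.3).** Among participants who complete colonoscopy, the five-level rating is to be modelled with proportional-odds ordinal logistic regression. If some categories are sparse, the outcome is to be split into adequate ("excellent or good*) versus inadequate (*fair, poor, or inadequate"). C.13 does not mention the nursing assessment or 'Adequate'-only records, and it gives no threshold for 'sparse'. It reserves the singular term for "the primary outcome of 12-month CRC screening test completion (yes/no"), which is a different outcome.

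**The concern.** One outcome has two stated definitions of 'inadequate'. They agree on four of the five grades and disagree on fair, and neither section mentions or explains the difference. If the fallback is used, the reported inadequate rate contradicts the definition in the measures section. A reader who takes the word from C.9 would misread the result.

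The two cut-points also respond to different changes. C.9 separates poor from fair and ignores the step from good to fair. The C.13 split does the reverse. If the choice between them is left open, it can be made after the ratings have been seen.

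The coding of individual records is open as well. A record that says only 'Adequate' could be grade 1, 2 or 3. For a completer who was sent home once and returned, C.9 does not say which attempt counts, and C.13 is silent on the nursing limb. These two gaps reach the planned ordinal model as well as the fallback.

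**Working it through.** The plan states no figure on this point, so there is none to reproduce. The check sets the two rules side by side and then sizes the difference.

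**Step 1. Classify each record under both rules.**

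| Record | C.9, endoscopist limb | C.13 fallback |
|---|---|---|
| excellent (1) | not inadequate | adequate |
| good (2) | not inadequate | adequate |
| fair (3) | not inadequate | **inadequate** |
| poor (4) | inadequate | inadequate |
| inadequate (5) | inadequate | inadequate |
| 'Adequate' only (1, 2 or 3) | not inadequate | no stated place |

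Among the graded records, only fair changes class.

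**Step 2. Difference in rates.** Write p3, p4 and p5 for the shares rated fair, poor and inadequate.

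- C.9, endoscopist limb: p4 + p5.
- C.13 fallback: p3 + p4 + p5.
- Difference: p3, the share rated fair. The documents do not give it.

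**Step 3. Expected numbers.** Tables 4 and 5 plan any-test completion of 44%, 20% and 5%, with 115 per group for analysis. C.12 enrols 150 per group.

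- 115 × (0.44 + 0.20 + 0.05) = 50.6 + 23.0 + 5.75 = 79.35.
- 150 × 0.69 = 103.5.

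These are expected counts under the planning rates, not limits. They equal the number of colonoscopy completers only if nobody is screened by FIT alone.

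With an assumed share rated fair of 10% to 30%, the number changing class is:

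- of 79.35: 7.9 to 23.8;
- of 103.5: about 10 to 31;
- of 39.7 (half of 79.35, if half are assumed to use FIT): 4.0 to 11.9.

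**Step 4. Which differences each rule sees.** Two invented comparisons, given as excellent or good / fair / poor or inadequate:

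- 60/30/10 against 60/10/30: C.9 inadequate is 10% against 30%, a gap of 20 points. C.13 inadequate is 40% against 40%, a gap of 0.
- 60/30/10 against 80/10/10: C.9 inadequate is 10% against 10%, a gap of 0. C.13 inadequate is 40% against 20%, a gap of 20 points.

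Neither cut-point is more sensitive in general. The five-level model uses both kinds of difference.

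**Step 5. 'Adequate'-only records.** Under C.9 such a record is not inadequate, whichever of grades 1 to 3 it stands for. In the five-level model it has three possible values. In the C.13 split, grades 1 and 2 fall on one side and grade 3 on the other. No rule in the documents chooses.

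**Step 6. Completers earlier sent home.** If the nursing limb applies once per participant, such a person is inadequate under C.9 whatever the later grade. If it applies per attempt and the completed attempt counts, the later grade decides. The text allows both readings. On the first, completers who were sent home and later graded 1 to 3 raise the C.9 rate, so the net difference in Step 2 would be smaller than p3.

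**The case against.** **The fallback may never be used.** This stands. The planned analysis is ordinal and has no cut-point, so the conflict over fair arises only if categories are judged sparse. How likely that is cannot be computed, because the documents give neither a rating distribution nor a threshold. They also do not say whether sparsity is judged overall or by arm, and that matters. Spread evenly over five grades, 79.35 is about 16 per grade, while the usual-care figure of 5.75 is 1.15 per grade. A proportional-odds fit, however, does not need every arm-by-grade cell to be filled.

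**C.13 is the analysis section, so its rule governs.** The documents state no order of precedence, and the C.9 rule stands under the heading for primary outcome measures. This objection does not remove the conflict.

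**An analyst could match the word 'Adequate' to the adequate group in C.13.** That is possible, so a reader who infers that such a record cannot be placed in the split goes too far. But C.13 limits its adequate group to excellent or good, while C.9 lets the word cover fair. The match would be a guess without a stated rule.

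**Stronger readings that the documents do not support.** A reader might infer that C.13 loses any difference between poor and fair. It does so only under the fallback. A reader might infer that the C.9 cut-point is the more informative one, but Step 4 shows that each misses what the other sees. A reader might also infer that a completer once sent home is certainly inadequate under C.9. That depends on reading the nursing limb per participant, which the text does not settle.

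**Conclusion.** The conflict is real and minor. C.9 and the C.13 fallback put fair in opposite classes, and nothing elsewhere in the documents reconciles them. If the fallback is used, the inadequate rate differs from the C.9 rate on the endoscopist's grade by the share rated fair. The numbers changing class rest on an assumed 10% to 30% for that share and on the planning rates. Only the algebra comes from the documents.

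The missing rule for 'Adequate'-only records, and the silence on which attempt counts after a patient is sent home, also affect the planned ordinal model. The documents do not say how often either occurs.

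The scope is the bowel-preparation part of H1.3. The 12-month any-test outcome, which drives the sample size, is unaffected.

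**What to change.** Before analysis, reconcile C.9 and C.13 so that one cut-point is used in both. The direct route is to align the C.13 fallback with the C.9 outcome definition. This is a matter of consistency with the stated definition, not a judgement on which cut-point is clinically right. If the sponsor confirms a different cut-point, it should be written into both sections.

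State how two kinds of record are coded, in the ordinal model and in the fallback: those that say only 'Adequate', and those of completers who were earlier sent home. Report the number of 'Adequate'-only records.

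The cost is wording plus one reported count. C.7 says that the information from the routine questions about preparation is already documented in the medical record, so no new data collection is needed.

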**C.8. Data Collection. (RQ-6, PC-2, PC-3)** Trained data collectors/interviewers who are employed by the Indiana University Center for Survey Research (CSR) will collect data via structured telephone interviews. Interviews will be conducted at baseline (T1), at 6 months post-baseline (T2), and at 9 months post-baseline (T3). If unable to reach participants when a phone interview is due, we will mail a letter to them requesting that they contact the CSR data collection team so that the interview may be completed. Reminder letters will be mailed to participants about 1 month before the T2 and T3 interviews are due. Process interviews will be conducted with participants assigned to the DVD intervention group approximately two weeks after mailing of the DVD. The baseline interview includes a question to confirm age eligibility and assesses the following: demographics, health literacy, health status, patient activation, CRC knowledge, CRC fear, cancer fatalism, colonoscopy-related procedural anxiety, social support, and media exposure. For both colonoscopy and FIT, the baseline interview asks questions about participants' experience with each test and readiness to screen by each test. Health beliefs for perceived CRC risk and colonoscopy and FIT perceived benefits, perceived barriers, and perceived self-efficacy are also collected. At completion of the baseline interview, participants will be randomized. People assigned to DVD or DVD + PN intervention groups will be told they will receive a DVD or instructions to access the website to view the program (based on their preference). Those in the tailored DVD + PN group will also be told they also will receive a phone call from the nurse navigator in about a week.

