**C.13. Data Analyses. (IR-3, IR-5, MD-3, MD-5, HT-1, HT-2, HT-3, HT-4)** Preliminary analyses will compare baseline demographic information across groups using means and standard deviations for continuous variables and frequency distributions for categorical variables. We will adjust for those characteristics in subsequent analyses if significant differences emerge at a conservative level for inclusion of a covariate ( $p < .20$ ). Characteristics of participants who drop out by 9 months will be compared with those who remain to determine what biases may exist. **(MD-4)** The above analyses will be conducted using ANOVA, chi-square tests, or exact or non-parametric equivalents. If there appear to be biases in dropout, we will conduct pattern mixture models analyses to see how the results could change based on the MAR assumption **(IR-5, MD-2, MD-3, MD-5)**. Primary analysis of outcomes will employ an intent-to-treat analysis; all participants will be included regardless of compliance with interventions. The main outcome, CRC screening completion with any test (FIT or colonoscopy) will be extracted from medical records for all participants, including those who drop out or are lost to follow-up. Intervention exposure will be measured and its effects will be accounted for in the intent-to-treat analysis. First, we will know whether participants viewed none, part, or all of the DVD. Second, we will document how many contacts PNs make to or on behalf of participants assigned to that group. These variables (viewed none/part/ or all of the DVD and number of navigator contacts) will be added as covariates in analyses. For all aims, sensitivity analysis will be conducted as needed for each outcome to assess the effects of the model assumptions on the results **(IR-5)**. Assumptions, such as normality of residuals, will be checked and appropriate modifications to the analysis plan applied if needed, such as transformations or use of non-parametric methods. From our prior studies, we expect missing data to be minimal (less than 2%) for subjects during participation. For missing data on scales, we will use mean imputation as long as two-thirds of the questions have been answered (or per validated instrument instructions, if otherwise). **(MD-2, MD-3)**

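### Procedural anxiety is measured at baseline, but Section C.13 does not specify the baseline score as a covariate in the anxiety model, and leaves the time point and analysis set open

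*Combined protocol and SAP*

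**What the plan says.** Section C.8 includes the scale in the baseline interview ("cancer fatalism, colonoscopy-related procedural anxiety, social support, and media exposure"). The Table 3 row "Colonoscopy-related procedural anxiety" is marked at T1, at 6 months (T2) and at 9 months (T3). The C.8 text lists anxiety in the 6-month interview, but its list for the 9-month interview leaves anxiety out.

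C.9 puts anxiety with the primary outcomes ("colonoscopy-related procedural anxiety and satisfaction with the CRC screening experience are described in this section"), although the scale itself is described under the secondary heading. H1.3 in Section C reads "Participants who receive either intervention who complete colonoscopy will have: 1) better quality of bowel preparation; 2) less anxiety about the procedure", with usual care as the comparator.

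For the model, C.13 says only "The outcomes of anxiety and satisfaction are continuous outcomes and will be modeled with linear regression". It names no covariate, time point or analysis set for anxiety. On adjustment in general, C.13 says "Preliminary analyses will compare baseline demographic information across groups" and then "We will adjust for those characteristics in subsequent analyses if significant differences emerge at a conservative level for inclusion of a covariate", with the threshold at p<.20. The only covariates it commits to outright arise after randomisation: "These variables (viewed none/part/ or all of the DVD and number of navigator contacts) will be added as covariates in analyses".

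**The concern.** In a randomised comparison of a continuous score, the baseline value of the same scale is the natural covariate. It is measured before assignment, it is already collected here, and it reduces residual variance to the extent that it predicts follow-up. Followed literally, the plan does not bring it in. The screening rule looks at demographics, and it tests for imbalance, which is the wrong criterion: the gain in precision depends on correlation with the outcome, not on whether the arms happen to differ.

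Two further gaps add to this. H1.3 concerns colonoscopy completers, a group formed after randomisation and plausibly selected in part by anxiety. C.13 does not say whether the anxiety model uses that group or everyone interviewed. Nor does it say which follow-up supplies the outcome.

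At stake are the precision of a listed outcome and a choice of covariates, time point and analysis set that could otherwise be made after the data are seen.

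**Working it through.** **Inputs from the plan.** 115 per arm for analysis (C.12); 0.50 SD and 99% power for continuous outcomes (text with Table 5); any-test completion of 44%, 20% and 5% (C.12, Tables 4 and 5); attrition of about 25% (C.12). The plan states no alpha for anxiety, so two-sided .05 is used.

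**Assumptions.** The correlation r of T1 with follow-up anxiety, taken as .2 to .6. For one scenario, half of those screened use FIT only.

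**1. The plan's own figure.** Two-sample power for 0.50 SD, either intervention against usual care, 230 vs 115, is 99.2%. This reproduces the stated 99%, but with all 345 participants analysed. A single pair of arms, 115 vs 115, gives 96.6%.

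**2. Gain from the baseline score.** Residual variance is multiplied by 1 − r², and the equivalent sample multiplier is 1/(1 − r²).

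| r | 1 − r² | variance saved | sample multiplier |
|---|---|---|---|
| .2 | .96 | 4% | 1.04 |
| .4 | .84 | 16% | 1.19 |
| .5 | .75 | 25% | 1.33 |
| .6 | .64 | 36% | 1.56 |

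**3. Everyone interviewed at T2.** The SE of either intervention against usual care, in SD units, is √(1/230 + 1/115) = 0.114 unadjusted. At r = .5 it is 0.114 × √.75 = 0.099.

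**4. Size of the completer subset.** Anxiety comes from interviews, so 115 per arm is the right base. The any-test rates give an upper limit on colonoscopy completers: .44 × 115 = 50.6, .20 × 115 = 23 and .05 × 115 = 5.75, or about 51/23/6. If half used FIT only, this becomes about 25/12/3.

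**5. Power among completers.** Either intervention against usual care, 0.50 SD, noncentral t with the model's error degrees of freedom. For 51/23/6 the unadjusted SE is √(1/74 + 1/6) = 0.424, and at r = .5 it is 0.424 × √.75 = 0.368.

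| r | power, 51/23/6 | power, 25/12/3 |
|---|---|---|
| none | 21% | 13% |
| .2 | 22% | 13% |
| .5 | 27% | 16% (15.5%) |
| .6 | 31% | 17% |

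For PN+DVD against DVD only, which is not an H1.3 contrast, 51 vs 23 gives 50% unadjusted and 62% at r = .5.

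**6. Can any other text bring the baseline score in?** The phrase in C.13 about continuous and categorical individual characteristics belongs to the logistic model for screening completion. The C.14 review of baseline characteristics leads to caution in interpretation, not to adjustment. C.8 speaks of assessing changes in anxiety at 6 months, but no change-score or baseline-adjusted analysis follows in C.13.

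**The case against.** The strongest reply is that the plan is silent and does not exclude adjustment. Linear regression can carry any covariate, and the C.8 wording about changes suggests that the investigators mean to use the baseline value. That stands as a limit on the point: a reader might infer that the plan rejects baseline adjustment, and the documents do not show this. The gap is one of prespecification.

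Second, the gain may be small. This is a state measure of present feeling, taken about 6 months apart, and for completers after the test itself. A low r is plausible, and at r = .2 only 4% of the variance is saved. This also stands, and is why the range starts at .2.

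Third, a reader might infer that adjustment would rescue H1.3, or would remove the bias from comparing completers. It does neither. With about 3 to 6 usual-care completers, power stays low at any assumed r. Conditioning on one measured score leaves selection into colonoscopy on other factors untouched.

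Fourth, the analysis set is not settled. C.13 states the completer restriction for bowel preparation; for anxiety it comes from the wording of H1.3. C.13 also promises an intent-to-treat primary analysis of all participants, so an all-participant anxiety model may already be intended. That is a reason to state it.

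Finally, putting every stratification factor into the completer model would not be free. Table 6 has 18 Hispanic patients among 1,151 non-completers of colonoscopy (1.6%), or about one in 80 trial completers. That objection is accepted in the fix.

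**Conclusion.** The point holds as a gap in prespecification. Anxiety is measured at T1 and is a listed outcome, yet nothing in C.13 makes the T1 score a covariate, and the demographic p<.20 rule does not reach it. Following the plan as written gives up 4% to 36% of residual variance, if r lies between .2 and .6; the documents do not supply r.

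The useful gain is in the model for everyone interviewed at T2, which also keeps the randomised comparison, subject to attrition. Among completers the gain against usual care is slight: 21% to 27% at r = .5 with the upper-limit counts, and less if many use FIT. The 99% power stated with Table 5 describes 345 analysed participants and does not carry over to a completer analysis.

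**What to change.** Amend C.13 as follows.

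- **Covariate.** Fit follow-up anxiety on arm plus the T1 anxiety score (ANCOVA), fixed in advance and whatever imbalance is observed.
- **Time point.** Name T2 as the outcome time point. Reconcile T3, which Table 3 marks for anxiety and the C.8 account of the 9-month interview leaves out.
- **Main model.** Use all participants interviewed at T2, adjusting also for the stratification factors (sex, race/ethnicity, age group), with sparse race/ethnicity levels collapsed. The scale asks about feelings when thinking about a colonoscopy, so people who have not had one can answer it.
- **Completer model for H1.3.** Report it with arm plus T1 anxiety only, labelled as a post-randomisation subset that remains open to selection bias.

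The cost is SAP wording, one degree of freedom for the T1 score and slightly more analysis work. No new data are needed.
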